#### 5.6 Statistical software employed

All analyses will be conducted using Stata/SE version 17 (or later), SAS version 9 (or later), or R version 4 (or later).

#### 6 SAFETY DATA

The frequency and percentage (%) of serious adverse events (SAE) and adverse events (AE) in the trial will be reported by treatment with the following details: the event type, severity assessment, expectedness and relatedness to intervention will also be summarised/analysed by treatment arm.

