Safety: All supervised sessions will be led by staff experienced in assessment, prescription and delivery of exercise for multi-morbid clinical populations. Pre- and post-exercise session poll questions will be completed by participants during each supervised session to capture any adverse events during the session and since the previous supervised session. Weekly troubleshooting after the live exercise sessions and the group behaviour change sessions will assess safety, progress, health, and any adverse effects. Participants will be advised to initially have another person nearby during exercise. If a participant fails to attend two consecutive intervention appointments a REGAIN practitioner will attempt to contact them via telephone or email in order to ascertain their welfare.

Intervention/control delivery: The multicentre REGAIN study will be delivered nationwide from a single central study 'hub'. The UHCW community exercise rehabilitation centre at Atrium Health delivers NHS cardiac, pulmonary, vascular, heart failure, cancer and other long-term condition rehabilitation services for Coventry and surrounding areas. Further, it is a clinical academic centre of excellence currently co-ordinating and delivering a number of nationally funded clinical exercise rehabilitation trials. The centre has the capacity, infrastructure and multi-disciplinary expertise to deliver the REGAIN study. Practitioners trained in the REGAIN intervention will be able to deliver the programme to groups of participants anywhere in the country using pre-recorded and live exercise and behaviour change sessions.

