4.2 Recording Adverse Events and Reporting Serious Adverse Events

4.2.1 Recording and reporting period

Intervention group: All AEs and SAEs that occur during or within 24 hours of a REGAIN live online session or an on-demand exercise session (supervised or unsupervised) should be recorded on the AE log by the exercise practitioner.

Usual care group: The usual care group will be asked about anything that might constitute a Serious Adverse Event at the time of their three-month follow-up. It will not be possible to collect a comparison dataset for the usual care group within this period without contaminating the control intervention. This is a pragmatic study and the participants will not be contacted during the intervention period, unlike the intervention group. It is important not to contact the usual care group more than is necessary so as not to introduce bias. We anticipate a low risk of adverse events arising from best practice usual care i.e. an NHS website and a single session of advice.

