4.2.3 Reporting Serious Adverse Events

All AEs should be assessed by the research practitioner to determine if they meet the criteria to be reported as a 'serious adverse event' as defined in section 4.1.2. If any of the adverse events meet this criteria, they will be reported to WCTU by emailing [contact] using the Serious Adverse Event form within 24 hours of becoming aware of it. If the 3 month questionnaire for a control group or REGAIN intervention group participant indicates events that may fulfil an SAE, then they should be contacted for further information and an SAE form completed if applicable.

A clinical assessment of whether the event has a causal relationship to the intervention should be made and recorded on the form by the practitioner. All SAEs should be reported irrespective of their relationship to the intervention unless they are exempt from reporting (see section 4.2.3.1).

For each **SAE** the following information will be collected:

- full details in medical terms and case description using CTCAE V5.0
- event duration (start and end dates, if applicable)
- action taken
- outcome
- seriousness criteria
- causality (relatedness to intervention), in the opinion of the practitioner

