5.1 Data collection and management

The CRFs and questionnaires will be developed by the Trial Manager in consultation with the CI, Statistician, Health Economist and other relevant members of the study team to collect all required study data.

All data will be entered directly by participants, REGAIN practitioners or WCTU study team members onto a secure online study database hosted by WCTU as outlined in the data management plan and in accordance with the Warwick SOPs. Data entered onto the online study database will be source data. This will be stored safely and securely. Personal identifiable information will be stored separately to other data collection forms. On all study-specific documents, other than the signed consent, the participant will be referred to by the study participant number, not by name.

For SAE reports, anonymised paper CRFs may be completed by UHCW staff and returned via email to WCTU for data checking and quality assurance purposes by study team members at WCTU and Sponsor representatives at UHCW. The participant will be referred to by the study participant number/code, not by name. If printed these forms will be stored in locked filling cabinets within WCTU accessible only to authorised staff from the study team. Electronic data will be stored in a secure area of the computer with access restricted to staff working on the study.

Various methods will be used to chase missing data including phone, text and email. Participants will receive an email notification and/or text message to remind them to complete the online questionnaires at each follow-up time point. If a participant has not completed a follow-up questionnaire within the anticipated time frame, the REGAIN study team will initially contact the participant via telephone to encourage them to complete the missing data and to provide support where required. A link to the study database may be provided via email to facilitate data completion. If data remain missing following this initial data chase, the REGAIN study team will contact the participant after a pre-defined period of time via telephone in order to attempt to collect core outcome measurements only (PROPr and EQ5DL). Where necessary a bilingual researcher will assist with the collection of missing data from participants who are non-English speakers. The procedures for managing this will be outlined in the data management plan and appropriate consent will be sought to contact participants.

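### SAP 6 sets adverse events side by side by arm, but non-serious events are collected only in the intervention arm and serious events by unequal routes

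*SAP*

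**What the plan says.** SAP 6 (Safety data) plans frequencies and percentages by arm: "serious adverse events (SAE) and adverse events (AE) in the trial will be reported by treatment". It adds that "the event type, severity assessment, expectedness and relatedness to intervention will also be summarised/analysed by treatment arm". It gives no denominator, does not separate events by how they were found, and does not mention that the arms are observed differently.

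The protocol sets out that difference:

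- **Intervention arm, sessions.** Protocol 4.2.1 has the practitioner log "All AEs and SAEs that occur during or within 24 hours of a REGAIN live online session or an on-demand exercise session". Protocol 2.9.1 adds active questioning: "Pre- and post-exercise session poll questions will be completed by participants during each supervised session to capture any adverse events during the session". The polls also cover the time since the previous supervised session. Protocol 4.2.2 describes how poll answers and volunteered information are followed up.
- **Control arm.** Protocol 4.2.1: "The usual care group will be asked about anything that might constitute a Serious Adverse Event at the time of their three-month follow-up". No route is described for non-serious events.
- **Both arms.** Protocol 4.2.3 provides a shared SAE route, opening with "If the 3 month questionnaire for a control group or REGAIN intervention group participant indicates events that may fulfil an SAE"; the participant is then contacted for details. Protocol 4.4 expects most deaths to be found in the GP records of 12-month non-responders, and makes no distinction by arm.

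On the intervention period, Protocol 4.2.1 concedes: "It will not be possible to collect a comparison dataset for the usual care group within this period without contaminating the control intervention".

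**The concern.** A by-arm harm table is read as a comparison of risks. Here, part of it compares how often people were asked. For non-serious AEs, the control column can only show zero, and a printed 0% will be taken to mean that no events happened. For SAEs, the intervention arm has two chances of detection and control has one, and SAP 6 would pool the sources.

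The primary estimate is untouched. What is at stake is the safety conclusion for a programme that Protocol 1.4 describes as suitable for immediate implementation nationally and internationally if the result is positive. The table could suggest a harm that is not there. Equally, a real excess could be dismissed as the product of closer questioning.

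**Working it through.** The documents give no event rates or detection rates for harms, so the plan has no figure of its own to reproduce here. The rates below are assumptions, shown as ranges.

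**Arm sizes.** SAP 2.8 reports 585 recruited and does not give the split. At the planned 1.03:1, control = 585/2.03 = 288 and intervention = 585 - 288 = 297.

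**Routes of detection**

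| | Intervention | Control |
|---|---|---|
| Non-serious AEs | session polls, practitioner log | none described |
| SAEs | session route and three-month questionnaire | three-month questionnaire |
| Deaths | GP record, plus any that staff learn of | GP record, plus any that staff learn of |

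**Non-serious AEs.** Control is 0/288 whatever happens to the participants. Take 6 recorded in 297 (2%). If all 585 shared one risk, the chance that all six fall in the intervention arm is C(297,6)/C(585,6) = 0.0167. The chance that all six fall in control is C(288,6)/C(585,6) = 0.0139. The two-sided Fisher p is 0.0167 + 0.0139 = 0.031. Five against zero gives p = 0.062. Fifteen against zero (5%) gives p = 0.00005. Six recorded events are therefore enough to pass the two-sided 0.05 threshold in SAP 5.5, even when true risks are equal.

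**SAEs.** Let the true risk be equal in both arms. Let q be the share of SAEs found by the questionnaire, the same in both arms, and s the share of the missed ones found by sessions. The true risk cancels:

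apparent risk ratio = [q + (1 - q)s] / q

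| q | s = 0 | s = 0.3 | s = 0.6 |
|---|---|---|---|
| 0.85 | 1.00 | 0.895/0.85 = 1.05 | 0.94/0.85 = 1.11 |
| 0.70 | 1.00 | 0.79/0.70 = 1.13 | 0.88/0.70 = 1.26 |

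For q = 0.70 and s = 0.6, the chance of a Fisher p below 0.05 with no true difference is 4.5%, 6.9% or 11.4% for a true SAE risk of 3%, 5% or 10%. With s = 0, meaning only the shared route is compared, it is 3.2%, 3.9% or 4.1%, and the risk ratio is 1.00. Restricting the comparison to the shared source therefore removes the bias in this model.

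**The case against.** The strongest reply is that SAP 6 promises a tabulation and not a test. SAP 2.7 confines null hypotheses to the primary and secondary outcomes. The protocol discloses the asymmetry and justifies it as avoiding contamination of the control arm. The dummy tables are in a separate document and may settle layout and denominators. Each SAE also receives two independent causality assessments (Protocol 4.2.4), so attribution does not rest on counts alone. Finally, the lean runs against REGAIN.

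Much of this stands. No test is named, the collection design is defensible, and the direction of the lean makes a concealed harm unlikely. It does not rescue the AE column, where a structural zero misleads with or without a p-value. The word 'analysed' in SAP 6 also leaves testing open, and the rule belongs in the SAP text.

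Three stronger readings are tempting, and the documents do not support them:

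- **That the SAE comparison is purely an artefact.** Protocol 4.2.3 applies the three-month questionnaire trigger to both arms. Protocol 4.2.1 rules out a control dataset only for the intervention period.
- **That the SAE risk ratio is inflated by at least 1.18.** A range of 1/0.85 = 1.18 to 1/0.70 = 1.43 requires near-complete capture in the intervention arm and 70-85% in control. Questionnaire non-response can affect both arms, the session log covers events during a session or within 24 hours of one, and people who do not attend have no session route.
- **That anyone reached by telephone is never asked about SAEs and is then counted as event-free.** In Protocol 5.1 the first call seeks all the missing data, and only a later call is limited to PROPr and EQ-5D-5L. The group left unasked is residual and of unknown size. SAP 6 states no denominator, so counting them as event-free is an inference from the all-randomised default in SAP 3.1.1.

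**Conclusion.** The point holds fully for non-serious AEs: the between-arm comparison is uninterpretable because control is zero by design. This needs no assumption about event rates; only the worked p-values depend on the assumed 297:288 split.

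For SAEs, ascertainment is differential but not void. Pooled counts lean towards more events with REGAIN. The illustrative risk ratio of 1.00-1.26 rests on equal true risk, equal questionnaire capture of 70-85% in both arms, and sessions finding 0-60% of what the questionnaire misses. The documents allow none of these to be fixed, so the direction is firmer than the size. A like-for-like SAE comparison is available from the shared sources, but SAP 6 does not specify it. The wording should be corrected before the safety analysis.

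**What to change.** Amend SAP 6 as follows.

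1. Present non-serious AEs descriptively for the intervention arm only. Show control as 'not collected', not 0%, and state that AEs are not compared between arms.
2. Tabulate SAEs by arm and by source of detection: session, three-month questionnaire, GP record. Base any between-arm comparison on the sources that both arms share:
   - SAEs identified through the three-month questionnaire, with those who answered the SAE question as denominator. Count an intervention SAE already reported in a session if the questionnaire would have covered it, since the participant may not report it twice.
   - Deaths from any source, among all randomised. A comparison limited to questionnaire respondents would lose fatal events.
3. State the ascertainment difference with the table.

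The rule on session-reported SAEs can leave a small asymmetry of its own, because it may restore events that a control participant would have forgotten. The breakdown by source lets a reader see how many are involved.

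The cost is SAP wording and a smaller comparative safety table; no new data are required. The SAE question could be added to any core-outcome telephone calls still to come. That is optional: it changes data collection, and because recruitment was already complete (SAP 2.8), it may come too late for many participants.

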#### 7 ADDITIONAL EXPLORATORY ANALYSIS

Any post-hoc analysis requested by the oversight committees, a journal editor or referees will be labelled explicitly as such. Any further future analyses not specified in the analysis protocol will be exploratory in nature and will be documented in a separate statistical analysis plan.

## 8 DEVIATION FROM ANALYSIS DESCRIBED IN PROTOCOL None yet.

9 REFERENCES

#### 9.1 Trial documents

Dummy tables can be found in the separate document.

